Safety objectives	Safety endpoints
To demonstrate the safety of exergames and COGNI-TRAcK over sham on the risk of: - accidental falls - adverse events	Time from randomization to the first accidental fall Proportion of patients with at least an adverse event from baseline to Week 8 and to Week 16

INTRODUCTION

Background and rationale for conducting the study

Cognitive impairment is common in people with multiple sclerosis (MS), frequently involving domains such as information processing speed, episodic memory, sustained attention, concentration and aspects of executive functions [1],[2]. Cognitive dysfunction can affect patients at any stage of the disease, from radiologically isolated syndrome to later phases of MS [3],[4].

There is no effective pharmacological treatment to manage cognitive impairment in MS [5]. Therefore, rehabilitation remains the only strategy to limit the impact of this dysfunction on quality of life. Encouraging results have been reported with computer-assisted training specifically focused on information processing, attention, and executive functions and performed with dedicated software [6]. Unfortunately, the time and costs of these cognitive rehabilitative programmes limit their applicability in the real life.

To increase the complexity of MS management, very often people with MS have coexisting cognitive and motor deficits and require both cognitive and motor rehabilitation. **Therefore, providing a single rehabilitative strategy that can address cognitive and motor issues remains highly desirable.**

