Exploratory endpoints: the MSIS-29 is a self-administered questionnaire measuring physical and psychological impact of MS from the subject's perspective; it has been reported to be more sensitive than other quality of life scales in detecting rehabilitation-induced changes [43]. The MFIS-21 is a self-administered questionnaire based on items derived from interviews with subjects with MS concerning how fatigue impacts their lives; it comprises three subscales (physical, cognitive, and psychosocial functioning) [44]. The WPAI:MS questionnaire measures employment status, absenteeism, impairment during work, overall work impairment and daily activity impairment [45].

Adherence

All eligible patients will receive a logbook to daily record the log of training (including time and type of game played). The logbook will be given at baseline visit and will be returned to the treating operator at the end of the training period (Week 8 visit). The machine log included in all the devices used in the present study allows double-check of adherence to intervention protocol.

Safety

Patients will be encouraged to contact the treating operator or another component of the study team (excluding the assessing operator) in case of AEs, for any question regarding the study protocol or technical problems. All eligible patients will receive a patient diary to record any AE occurring during the study and the occurrence of accidental falls, defined as an unexpected contact of any part of the body with the ground that not results from loss of consciousness. The patient diary will be given at baseline visit and will be returned to the treating operator at the end of the follow-up period (Week 16 visit).

AEs will be reported according to the World Health Organization (WHO) guidelines for Good Clinical Practice (GCP) in biomedical research on human subjects [46]. AEs are graded as mild (minimal or no treatment required and no interference with daily living activities), moderate (may require treatment and cause some interference with functioning), severe (systemic drug or other treatment required, interruption of daily living activities), or life-threatening (immediate risk of death).

Predictors of outcomes

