No pharmacological treatment is strictly forbidden; however, patients are encouraged to not start pharmacological treatments that can potentially impact on cognition, namely antidepressants, dalfampridine, nabiximols, modafinil, amantadine, dopamine-agonists.

Steroid administration due to MS relapse or any symptomatic drug initiation due to any MS-related symptom should be considered as an AE.

Patients are encouraged to not start any other type of physiotherapy or rehabilitation during the study period, but they are encouraged to continue his/her physiotherapy or rehabilitation program if started at least 3 months before the study enrolment.

STATISTICAL PLAN

Sample size estimation

Overall, we will randomize **126 patients** (considering even a 20% drop-out rate), based on two previously published studies that have found:

- (i) a significant effect of an home-based cognitive training using the [name]® Brain Training that promoted an about 8-point mean increase at SDMT score (with respect to wait-list group) [53];
- (ii) a significant effect of adaptive COGNI-TRAcK that promoted an about 8-point mean increase at SDMT score (with respect to a sham intervention) [24];
- (iii) a 50%-difference in proportions of responders (10/14 versus 3/14 in adaptive COGNI-TRAcK group and sham COGNI-TRAcK group, respectively) [24], according to a responder definition of SDMT change approximating 4 points or 10% in magnitude [28].

For the non-inferiority comparison, the null hypothesis is that the intervention with exergames is inferior to adaptive COGNI-TRAcK, while the alternative hypothesis is that the intervention with exergames is non-inferior to adaptive COGNI-TRAcK by a pre-defined amount of SMDT score.

If there is truly no difference between exergames and adaptive COGNI-TRAcK, then 35 patients per arm are required to ensure, with a statistical power of approximately 85%, that the lower limit of a one-sided 95% confidence interval (or equivalently a 90% two-sided confidence interval) will be above the predefined non-inferiority margin of 8-point change in SDMT.

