For the superiority comparison, the null hypothesis is that the intervention with adaptive COGNI-TRAcK is not superior to sham COGNI-TRAcK, while the alternative hypothesis is that the intervention with adaptive COGNI-TRAcK is superior to sham COGNI-TRAcK in increasing the proportion of responders as afore defined. Enrolling 35 patient per arm will ensure a more than 95% power in detecting a statistical significance between-group difference of 50% at two-sided alpha level of 5%.

Statistical analysis

All analysis will be based on the intention-to-treat principle using the fully analysis dataset including all randomized patients. Missing data will be handled by multiple imputation method, with the assumption that some data will be missed completely at random.

Efficacy analyses: efficacy data will be analyzed by parametric and/or non-parametric Repeated Measures Analyses of the Variance (RM-ANOVAs) with effect size estimation. In each analysis, we will consider as dependent variable all measures or score derived from study assessments; the three study visits (Baseline, Week 8 and Week 16) as within-subject factors; and intervention arms (exergames, adaptive COGNI-TRAcK and sham COGNI-TRAcK) as between-subject factors. Effect sizes will be estimated as Cohen's F-squared, rated as small, medium, and large for values of 0.02, 0.15, and 0.35, respectively [54].

Safety data regarding time to first accidental falls will be analyzed as time-to-event data by Kaplan-Meier curves and Log-Rank test with a factor for intervention arms.

Safety analyses: data regarding the occurrence of adverse events during the intervention period and the follow-up period will be analyzed by the Chi-squared test comparing the independent distribution of events according to intervention arms.

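### The only fall-specific analysis uses time to first fall, so repeat falls that the diary can capture enter no stated analysis; a fall-rate comparison is a cheap addition.

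*Protocol*

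**What the plan says.** The safety table in the Protocol Synopsis sets an objective on the risk of accidental falls and names the endpoint as "Time from randomization to the first accidental fall". Under Statistical plan, Statistical analysis, the method is fixed: "Safety data regarding time to first accidental falls will be analyzed as time-to-event data by Kaplan-Meier curves and Log-Rank test", with intervention arm as the factor.

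The second safety endpoint is "Proportion of patients with at least an adverse event from baseline to Week 8 and to Week 16". For it, "data regarding the occurrence of adverse events during the intervention period and the follow-up period will be analyzed by the Chi-squared test". It is not specific to falls, and it too reduces each patient to yes or no.

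Under Study assessments, Safety, patients receive a diary to "record any AE occurring during the study and the occurrence of accidental falls", to be handed back at Week 16. The end-of-study procedures (Week 16 visit) agree with that. The table under Study plan and timing of procedures instead shows the diary returned at Week 8.

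No expected fall rate, number of fallers or power for falls is given. The section on the pre-planned significance level sets two-sided 0.025 for the comparisons of the two active arms with sham.

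**The concern.** A patient who falls once and a patient who falls every week count the same in the log-rank test if their first falls come on the same day. The same holds in the adverse-event table. Exergames here are balance-board games played at home with minimal assistance, and the Protocol's rationale for endpoints gives falls particular attention. For a harm endpoint the costly error is a missed excess. If exergames raised the number of falls mainly among people who fall repeatedly, no stated comparison would register those extra falls. The method is written into the Protocol, so this is a stated choice and not a detail left open.

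**Working it through.** **1. Do repeat falls enter any stated analysis?** The fall endpoint is the first fall; its test is the log-rank. The other safety endpoint is at least one adverse event; its test is chi-squared. Neither uses a count, so the answer is no.

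**2. Inputs.**
- From the Protocol: 126 patients in three equal arms, 126/3 = 42 per arm (the Synopsis total of 132 would give 44; the evaluable number is 35); two-sided 0.025, z = 2.241; diary over 16 weeks.
- Assumed, because the Protocol gives no value: control mean μ0 of 0.3 to 2 falls per patient per 16 weeks, rate ratio 2, negative binomial dispersion k = 1 (range 0.5 to 4).

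There is no fall figure in the Protocol to reproduce.

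**3. Closed-form example, one active arm against sham, μ0 = 1, μ1 = 2, k = 1, full follow-up.**

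First fall:
- Share with at least one fall, p = 1 − (1 + kμ)^(−1/k): p0 = 0.500, p1 = 0.667.
- Implied first-fall hazard ratio, ln(1 − p1)/ln(1 − p0) = 1.099/0.693 = 1.585. The doubled rate is already attenuated.
- Expected fallers, 42 × (0.500 + 0.667) = 49.
- Power = Φ(√(49/4) × ln 1.585 − 2.241) = Φ(1.61 − 2.24) = 26%.

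All falls:
- var(log rate ratio) = (1/μ0 + 1/μ1 + 2k)/n = (1 + 0.5 + 2)/42 = 0.0833, so SE = 0.289.
- Power = Φ(0.693/0.289 − 2.241) = Φ(0.16) = 56%.

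Expected falls in the two arms are 42 × (1 + 2) = 126, so the first-fall analysis leaves 1 − 49/126 = 61% of them unused.

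**4. Across fall rates** (42 per arm, k = 1, doubling sustained for 16 weeks). The simulation adds 20% of patients leaving early; test size was close to nominal.

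| Control falls per 16 weeks | Closed form: first / all | Simulation: first / all |
|---|---|---|
| 0.3 | 22% / 29% | 22% / 27% |
| 0.6 | 26% / 45% | 28% / 39% |
| 1 | 26% / 56% | 29% / 52% |
| 2 | 23% / 68% | 30% / 69% |

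**5. Sensitivity.**
- *Clustering*, at 1 fall per patient (closed form): k = 0.5, 40% against 73%; k = 2, 15% against 37%; k = 4, 9% against 22%. The k = 4 gain is not secure: in simulation the Wald rate test rejected about 4% under no effect against a nominal 2.5%, and a pooled-variance rate test reached only 13% against 9% for the log-rank.
- *Smaller arms*, 35 per arm, k = 1 (closed form): 18% against 24% at 0.3 falls, 22% against 48% at 1.
- *Excess only in weeks 0-8, all 16 weeks counted* (simulation): the gain shrinks to 2 to 8 points.
- *Excess only in weeks 0-8, both tests limited to weeks 0-8* (simulation): 24% against 38% at a 16-week rate of 1, and 34% against 56% at 2. The gain returns when the window matches the exposure.

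**The case against.** Time to first fall is a coherent, pre-specified measure of the risk of falling, which is what the objective names. It is inefficient in some settings, not wrong, and an analysis plan that is not shown could add a rate analysis. Repeat falls are not lost: they stay in the diary, the visit procedures treat falls as adverse events, and an independent committee with access to treatment codes reviews the safety data. All this stands. It does not alter the fact that the endpoint and test the Protocol does fix use only the first fall.

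A reader might infer that an excess of falls under exergames is in general much less likely to be detected, or that a doubled rate would pass as no difference. The documents do not support that. They give no fall rate, and the large gains need both about 0.6 or more falls per patient and an excess that persists after the device is returned at Week 8. An excess limited to the training weeks is at least as plausible, and counting all 16 weeks then brings little. The simulated falls also follow the model that the rate test fits, which favours it.

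Two further cautions stand. Repeat-fall counts depend on self-report by patients selected for cognitive impairment. And most scenarios leave both tests with modest power, so the change improves the comparison without making it decisive.

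**Conclusion.** The point holds as an improvement to a valid analysis. Repeat falls enter no stated comparison, although the diary can capture them and falls are a named safety objective. With 42 per arm, two-sided 0.025, dispersion 1 and a doubling sustained over 16 weeks, counting all falls raises power by 5 points at 0.3 falls per patient (27 − 22), 11 at 0.6 (39 − 28), 23 at 1 (52 − 29) and 39 at 2 (69 − 30). The rate, dispersion, rate ratio and persistence of the excess are all assumptions. The gain is small when falls are rare, uncertain under very strong clustering, and 2 to 8 points when a training-period excess is diluted over 16 weeks. The Protocol nowhere equates non-significance with safety, but at these sizes the report should not do so either. The primary endpoint is unaffected.

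**What to change.** 1. Synopsis, safety endpoints: add the number of accidental falls per patient.
2. Statistical analysis: keep the Kaplan-Meier curves and log-rank test. Add a negative binomial comparison of fall rates with log follow-up time as offset, reporting rate ratios with confidence intervals for each active arm against sham, separately for weeks 0-8 and for the full 16 weeks. The separate training-period estimate is needed because a 16-week count dilutes an excess that ends with training.
3. Reconcile the diary's return date: Week 8 in the visit table, Week 16 in the Safety section and the end-of-study procedures. The 16-week count depends on it.
4. Check that the diary form (an appendix, not shown) records the date of each fall.

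The cost is one endpoint line and one or two sentences of analysis; the diary is already in use. The downside is reliance on complete diary entry of repeat falls by cognitively impaired patients and on a model for overdispersion. Power remains modest, so the interval for the rate ratio should carry the interpretation.

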Patients with MS, regardless of disease course, who fulfil all inclusion criteria and none of the exclusion criteria, will be randomized in a 1:1:1 ratio to exergames or adaptive COGNI-TRAcK or sham COGNI-TRAcK. This study includes two periods (training period and follow-up period) and three visits (see the **FIGURE** below):

- on Week 0, at study enrolment/randomization (baseline visit);
- on Week 8 (+/- 5 days), i.e. after the end of the 8-week training period (Week 8 visit);
- on Week 16 (+/-5 days), i.e. at study termination after the 8-week post-training follow-up period (Week 16 visit).

Eligibility criteria

For inclusion:

- (i) age between 18 and 55 years (inclusive);
- (ii) cognitive impairment, defined as failure in the SDMT, defined as a corrected score less than 38, i.e. below the 5th percentile of normative value [31];
- (iii) Expanded Disability Status Scale (EDSS) score between 2.0 and 5.5 [32];
- (iv) ability to stand upright for at least 180 seconds without any support;
- (v) ability to understand and comply with study requirements;
- (vi) ability to provide a valid informed consent before any study procedure.

For exclusion:

- (i) relapse in the previous 6 months;
- (ii) initiation of disease-modifying or symptomatic treatments or physiotherapy programme in the 3 months prior to study entry;
- (iii) any medication/physiotherapy changes occurring over the previous 3 months;
- (iv) significant visual impairment, defined as a Visual System scoring more than 2 at the Kurtzke Functional Systems Score [32];
- (v) clinically relevant depression, defined as Beck Depression Inventory-II (BDI-II) score equal or more than 14 [33];
- (vi) overt dementia, defined as an adjusted Mini Mental State Examination (MMSE) score equal or less than 24 [34];
- (vii) history of epilepsy or seizures;
- (viii) any medical condition, including musculoskeletal disorders that can interfere with the study conduction.

Randomization procedure

Randomization codes will be computer-generated in blocks of six to ensure an approximate 1:1:1 balance between the three arms. Randomization codes will be assigned at baseline visit sequentially within each center as patients become eligible for randomization by an independent organization not involved in study conduction. Once a block is exhausted, the next available block will be allocated to a center upon the next randomization.

Blinding

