Predictors of outcomes: logistic regression analyses will test if the achievement of a clinically relevant change in the pre-planned endpoints is predicted by scores derived from CRIQ, HLAQ and TCI, after controlling for a set of baseline covariates including sex, age, disease duration, EDSS score, performance on the explored task. For those endpoints lacking of a definition of clinically relevant change, we will adopt Analyses of Covariance (ANCOVAs) with immediate post-training score as dependent variables, intervention arm as fixed factor and a set of baseline covariates including sex, age, disease duration, EDSS score, baseline performance on the explored task, as well as scores derived from CRIQ, HLAQ and TCI as covariates of interest.

Pre-planned statistical significance level

Exergames and adaptive COGNI-TRAcK will be compared with sham COGNI-TRAsK as placebo-analogue arm. Therefore, all analysis will be corrected with Bonferroni adjustment for multiple comparisons of two-sided tests, giving a two-sided significant p-value of 0.025.

Interim analysis

An interim analysis will be conducted when at least 50% of the estimated sample size will complete the 8-week intervention period.

STUDY GOVERNANCE AND OVERSIGHT

Steering committee

The steering committee shall comprise the Principal Investigator (PI) and all the co-investigators reported in this study protocol.

The steering committee will be responsible for the overall design, interpretation, supervising and reporting (presenting at national and international congresses and publishing in peer-reviewed journals). Members of steering committee will be also responsible for providing clinical guidance on study implementation and conduct in their respective sites.

Data Monitoring

An independent Data Monitoring Committee (DCM) will be appointed to review the overall conduct of the study, with particular attention to eligibility criteria, randomization, and collection of efficacy and safety data. The DCM will have access to the individual treatment codes while the study is ongoing; therefore, if DMC expresses safety concerns, appropriate information will be sent to the PI, regulatory authorities and study funder Associazione Italiana Sclerosi Multipla (AISM).

The DCM is also responsible for ensuring the maintenance of blinding and integrity of the study.

ETHICAL AND REGULATORY REQUIREMENTS

Ethical conduct of the study

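### The Bonferroni threshold of 0.025 is written to cover every analysis, so the falls and adverse-event tests carry a correction they do not need, and a non-significant safety result becomes more likely

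*Protocol*

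**What the plan says.** The Protocol section on the pre-planned significance level gives its reason first: "Exergames and adaptive COGNI-TRAcK will be compared with sham COGNI-TRAsK as placebo-analogue arm". It then draws the consequence: "all analysis will be corrected with Bonferroni adjustment for multiple comparisons of two-sided tests, giving a two-sided significant p-value of 0.025". The rule comes after the efficacy, safety and predictor analyses have all been described, and it names no exception.

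The safety tests are set out under Statistical analysis. Time to first fall is analysed by Kaplan-Meier curves and a log-rank test with arm as the factor. Adverse-event data "will be analyzed by the Chi-squared test comparing the independent distribution of events according to intervention arms". Neither test has a significance level of its own.

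In the synopsis, the safety objective reads "To demonstrate the safety of exergames and COGNI-TRAcK over sham on the risk of" accidental falls and adverse events. No section states how large an excess over sham would still be acceptable.

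**The concern.** A Bonferroni correction buys protection against false positives at the price of more false negatives. For efficacy that is the right trade, because the error to guard against is a false claim of benefit. For falls and adverse events the more serious error is to overlook a real excess, and the correction makes that error more likely.

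The correction also does not fit the tests. Dividing 0.05 by two answers the question of two comparisons with sham. A single log-rank or chi-squared test across three arms is one test, and its own type I error is already controlled at its nominal level. Applying 0.025 there costs sensitivity and resolves no multiplicity within that test. Falls and adverse events in two periods do make several safety tests, but that is not the reason the protocol gives.

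What is at stake is the final safety comparison. The objective is to demonstrate safety, the only tools named are tests for a difference, and no tolerable excess is given. A non-significant result is then easily taken as the demonstration, and a stricter threshold makes that result more frequent.

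**Working it through.** **1. The plan's own figures.** 0.05 / 2 = 0.025, so the threshold reproduces exactly for two comparisons. The superiority statement is "Enrolling 35 patient per arm will ensure a more than 95% power", using the responder rates "10/14 versus 3/14 in adaptive COGNI-TRAcK group and sham COGNI-TRAcK group, respectively", that is 71.4% against 21.4%. With 35 per arm the two-proportion power is 99.5% at two-sided 0.05, which agrees with the protocol, and 98.8% at 0.025. The responder comparison therefore loses under one point from the correction.

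**2. Inputs for safety.** Sample size estimation gives 126 randomized, and allocation is equal (patients "will be randomized in a 1:1:1 ratio to exergames or adaptive COGNI-TRAcK or sham COGNI-TRAcK"), so there are 126 / 3 = 42 per arm. The synopsis total of 132 would give 44, which changes little. The documents contain no adverse-event or fall rates, so **every rate, hazard ratio and event count below is an assumption**. The excess is placed on one active arm only. Critical values at 0.05 and 0.025 are 1.960 and 2.241 for a two-sided normal test, and 5.991 and 7.378 for chi-squared with 2 degrees of freedom.

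**3. Pairwise adverse-event test, active against sham.** The statistic is Z = (p1 − p0) / √[2p̄(1 − p̄)/n]. Power is the summed binomial probability of all outcomes with Z above the critical value.

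Hand check by the normal approximation for 20% against 40%, with p̄ = 0.30:
- 0.20 × √42 = 1.296; √(2 × 0.30 × 0.70) = 0.648; √(0.16 + 0.24) = 0.632.
- At 0.05: (1.296 − 1.960 × 0.648) / 0.632 = 0.04, power 52%.
- At 0.025: (1.296 − 2.241 × 0.648) / 0.632 = −0.25, power 40% (exact 41%).

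**4. Three-arm chi-squared test, closer to the protocol's wording.** The noncentrality is λ = n Σ(pᵢ − p̄)² / [p̄(1 − p̄)]. For 20/20/40%, p̄ = 0.2667 and λ = 42 × 0.02667 / 0.1956 = 5.73. Power comes from the noncentral chi-squared distribution with 2 degrees of freedom.

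| Assumed rates (sham, active) | Pairwise, exact: 0.05 / 0.025 | Three-arm: 0.05 / 0.025 |
|---|---|---|
| 20%, 40% | 52% / 41% | 56% / 45% |
| 10%, 25% | 46% / 33% | 50% / 39% |
| 30%, 50% | 49% / 36% | 49% / 38% |

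The loss is about 11 to 14 points pairwise and 11 points for the three-arm test. Over a wider set of assumed rates (5–30% on sham, 15–50% on active, 35 to 44 per arm), the normal approximation gives a pairwise loss of about 9 to 12 points.

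**5. Falls, pairwise log-rank.** Power = Φ(|ln HR| × √(d/4) − z), where d is the number of events. For a hazard ratio of 2 with 30 events, 0.693 × √7.5 = 1.898, giving 48% at 0.05 and 37% at 0.025. For a hazard ratio of 3 with 20 events, power is 69% and 59%. Over hazard ratios of 1.5 to 3 and 15 to 40 events, the loss is about 4 to 11 points.

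**The case against.** The best defence is that the sentence is loosely drafted and meant for efficacy. Its premise is the two comparisons with sham, while the safety tests are described across all arms. Nor is the rule followed literally elsewhere: superiority is powered for a "between-group difference of 50% at two-sided alpha level of 5" per cent, and non-inferiority uses a one-sided 95% interval. This may well be the intention. But no section says so, and the safety objective is itself framed as both active arms over sham, so the literal reading remains open and needs closing.

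Second, the threshold is not the main weakness. In the table, 44% to 54% of such excesses are missed at 0.05 anyway. That stands. Lifting the correction recovers only 11 to 14 points, which is why the remedy cannot stop at the alpha level.

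Third, a reader might infer that the plan contains a rule by which safety is concluded whenever p exceeds 0.025, so that it tilts the decision towards the interventions. The documents do not support that. No section states such a rule. Adverse events and falls are collected by diary, adverse events are graded by severity, and an excess with p = 0.03 would still show in the Kaplan-Meier curves and the event counts. Under Data Monitoring, an independent committee has access to treatment codes and can report safety concerns without reference to any p-value. The problem is confined to the formal comparison and how it may be read.

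Fourth, the assumed rates may be too high: the risk-benefit section cites pilot work with no or minor adverse events and no increase in falls. The rates are illustrations, and the size of the loss depends on them; its direction does not.

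**Conclusion.** The point holds in a limited form. As written, the 0.025 threshold extends to the falls and adverse-event tests, where the two-comparison rationale does not fit the overall tests described. With 42 per arm and assumed rates such as 20% against 40%, this costs about 11 to 14 points of power to flag a real adverse-event excess, from 46–56% down to 33–45%. For falls the loss is about 4 to 11 points over the assumed hazard ratios and event counts. The efficacy responder comparison is almost untouched.

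The consequence is a greater chance of a non-significant safety result that could be mistaken for demonstrated safety. It is not evidence that the protocol would declare safety on that basis, nor that patients go unmonitored during the trial. Low power at 0.05 remains the larger limitation.

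**What to change.** - **Pre-planned statistical significance level:** state that the Bonferroni correction applies to the efficacy comparisons of each active arm with sham, and not to the safety analyses.
- **Statistical analysis, safety:** add that falls and adverse events will be reported for each active arm against sham as a hazard ratio or risk difference with an unadjusted 95% confidence interval.
- **Safety objectives in the synopsis:** replace the aim of demonstrating safety with one of estimating the risk of falls and adverse events relative to sham, so that non-significance is not taken as proof of safety. The intervals then describe what the data can and cannot exclude. A formal safety conclusion from their upper limit would need a stated tolerable excess, which the protocol does not have.

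This is one sentence in each of three places, with no new data, visits or patients. The price is a somewhat higher chance of a false safety signal.
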